9.5 Subject Monitoring

Subjects will be monitored using PRO-CTCAE. The principal investigator and sponsor will also select a committee of up to 4 qualified individuals to serve on a Data Safety and Monitoring Board. The DSMB will receive regular updates on adverse events and will have access to unblinded data should they decide to explore whether a frequent or serious adverse event is associated with the study drug. Assessment of suicidal ideation and/or behavior will be conducted using the Columbia-Suicide Severity Rating Scale (C-SSRS).

9.6 Outcome Measures

Primary Outcome Measures

The primary outcome measures will be change from baseline of tremor power by digital spirography for drug vs. placebo.

Secondary Outcome Measures

The secondary outcome measures will include the TETRAS, CGI, PRO-CTCAE, plasma concentrations of CBD/THC, Common Toxicity Criteria for adverse effects, and Columbia-Suicide Severity Rating Scale.

9.7 Sample Size Estimation

A power analysis was performed to estimate the minimum number of subjects for enrollment. We assumed the following: Significance (p<0.01 or p<0.05, corrected), Power=0.80, minimum expected group difference of 15%, and an estimated standard deviation of 10%. Based on these assumptions, we will require a minimum of 14 participants to complete the study. For purposes of this study, 16 subjects will be enrolled and will complete all aspects of this study. To account for drop-outs due to various causes, we plan to have an accrual ceiling of 20 subjects.

9.8 Data Analysis

Data analysis will be performed by a consulting statistician who will also provide guidance in the final experimental design. Each subject will serve as their own control. We will collect baseline tremor severity using the various outcome measures described and will utilized paired-sample t-tests for evaluation of statistical significance between drug and placebo vs. baseline. Descriptive statistics will also be performed in an exploratory fashion.

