6. SPECIFIC AIMS

The present study seeks to assess the efficacy and tolerability of TILRAY TN-CT120LM (FDA IND#137400), a pharmaceutical-grade formulation containing THC and CBD, vs. placebo in an Essential Tremor patient population. The study is intended to collect pilot data to determine whether larger studies are warranted and assist in their future design.

Aim 1: To determine if short-term exposure to orally administered THC/CBD improves tremor amplitude in ET patients. Hypothesis 1: ET patients receiving THC/CBD orally will have reduced peak tremor power (compared with their own baseline measures) by accelerometry and spirography vs. placebo.

Aim 2: To determine acute and short-term tolerability of orally administered THC/CBD. Hypothesis 2: ET patients receiving THC/CBD orally will be associated with more frequent ratings of sedation on the Common Toxicity Criteria compared with placebo.

Aim 3: To characterize the relationship between THC/CBD exposure with clinical response (i.e. tremor amplitude) to define a plausibly useful dose range for evaluation in future confirmatory clinical trials.

BACKGROUND AND SIGNIFICANCE 7.

7.1 There is a great medical need for a more effective treatment for essential tremor.

Essential tremor (ET) is traditionally defined as bilateral, generally symmetric postural and kinetic tremor of the upper extremities that is not attributable to identifiable causes, and has been present for at least 5 years. A meta-analysis of prevalence studies indicates that 0.4 to 0.9% of the general population has ET. The figure rises to 4.6 to 6.3% among those 65 years or older (Louis and Ferreira, 2010). ET is a common cause of embarrassment, social withdrawal, disability, and loss of occupation.

The most commonly utilized medications for ET are propranolol, primidone, topiramate, gabapentin, and benzodiazepines. Unfortunately, the long-term efficacy and tolerability of current medications leave much to be desired. If one surveys hundreds of ET patients, it is found that one-third have stopped all ET medications, even those with the most severe tremor. In other words, many of the most disabled ET patients have abandoned the search for a drug that can help them. Over half the patients who try primidone, propranolol, diazepam or topiramate end up stopping them, and the percentage is higher with other anti-ET medications (Louis et al., 2010).

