The starting dose, titration schedule and target dose were selected based on safety, tolerability and efficacy data reported in previous studies using cannabinoids to treat pain (Langford et al., 2013; Portenoy et al., 2012; Johnson et al., 2010). Adverse effects will be inventoried at each study visit. If the patient or investigator feel that the higher study drug dose is causing troublesome side effects, the dosage may be lowered. Food intake can affect systemic exposure of cannabinoids (Zgair et al. 2016). Subjects will be advised to schedule their dose at a similar time every morning after breakfast to maintain similar systemic exposure throughout the study. Regular reminders will be provided to subjects to ensure they are taking the study drug post-meals. During study visits when drug is administered, subjects will be provided with a standardized FDA high-fat, high-calorie meal prior to taking the study drug.

DOSE TAPER AND WASHOUT

After completing a 2-week course on 15/300 mg/day of THC/CBD or placebo, subjects will return on this dose for assessment and completion of the various measures detailed in Appendix 1. After completion of this visit, subjects will taper from the treatment gradually over 1-week, in similar fashion to the dose titration up to the target dose. Subjects will then complete a 3-week washout period prior to being crossed-over to the alternate arm. This is to allow subjects to return to their baselines. The duration selected is conservative and takes into consideration the known elimination half-life of THC/CBD.

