9.4 Assessment Measures

DIGITAL SPIROGRAPHY

This functional measure of kinetic tremor in subjects with ET has been validated by a group at NINDS, including [name]. In this technique, the subject is asked to draw a spiral between the loops of a pre-printed spiral with an unsupported hand, proceeding from inside the figure to outside. This measure offers an objective measure of functional tremor, and may enable detection of efficacy with fewer subjects (Haubenberger et al.,

2011). As this methodology is recent, it has not yet found widespread application ET clinical trials. Subjects with severe tremor who have difficulty keeping the inking stylus in contact with the paper are not suited for this test. Based on our experience, we consider this scale to be appropriate as a primary outcome measure.

ACCELEROMETRY

This functional measure of tremor allows objective measurement of postural tremor. During this task, subjects are asked to maintain each arm in an isometric posture with the arm in a 'winged' position in front of the chest. Tri-axial accelerometers are used to collect the tremor frequency and magnitude. Tremor severity is derived from the time domain of a Fourier transformation. This measure allows for standardization across time and 1-minute of data is collected for each limb to minimize variability.

TETRAS

This scale evaluates tremor of various body parts during postures, kinesis and tasks. Items are scored from 0 to 4, with 4 representing the highest degree of severity. The maximum score is 64 (Elble et al., 2012). Although this scale was recently published, it is a refinement of the long-used Fahn-Tolosa-Marin scale. Based on the authorship, this scale has clearly received widespread endorsement from the opinion leaders in the field of essential tremor. To achieve maximum credibility with any result from this clinical trial, it is appropriate to include this scale as a second primary measure. One difficulty with on-site blinded examiners is that they may be prone to placebo effects in their ratings, as they are aware which visit is baseline and which is the treatment visit, although the latter may be with placebo or active drug. To eliminate such order effects, we will videotape the subject undergoing this rating and provide the videos to a minimum of two blinded raters unfamiliar with which visits are baseline and treatment visits.

GLOBAL IMPRESSION OF CHANGE

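### Section 9.8 analyses a two-period cross-over with plain paired t-tests; adding a period term is a cheap improvement, because nothing else in the plan adjusts for period

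*Combined protocol and SAP*

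**What the plan says.** Section 9.3 describes two treatment arms assigned from a prepared randomisation list, then a taper and washout: "Subjects will then complete a 3-week washout period prior to being crossed-over to the alternate arm". The allocation ratio and any blocking are not stated.

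Section 9.6 defines the primary outcome as "change from baseline of tremor power by digital spirography for drug vs. placebo". Hypothesis 1 in section 6 asks for the same contrast: "reduced peak tremor power (compared with their own baseline measures) by accelerometry and spirography vs. placebo".

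Section 9.8 gives the only efficacy test: "will utilized paired-sample t-tests for evaluation of statistical significance between drug and placebo vs. baseline". Period, sequence and carry-over terms appear nowhere in the document. Section 9.4 takes a step against order effects, but only for the TETRAS video ratings: "To eliminate such order effects, we will videotape the subject undergoing this rating".

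Appendix 1 marks spirography at screening, Visit 4 (day 22) and Visit 8 (day 71). There is none at Visit 5, where the second period starts.

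**The concern.** In a two-period cross-over, each subject's drug-minus-placebo difference contains the treatment effect plus or minus whatever changed between the periods, with the sign set by the order received. Practice at the spiral task, changed expectations or drift over seven weeks could all contribute. A plain paired t-test treats that systematic component as random error. If the two sequences finish with unequal numbers, part of it also enters the estimate.

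Section 6 says the study is "intended to collect pilot data to determine whether larger studies are warranted and assist in their future design". For that purpose the estimate, its interval and its SD matter as much as the p-value.

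**Working it through.** **Inputs.** Section 9.7 gives a "minimum expected group difference of 15%, and an estimated standard deviation of 10" percent, power 0.80, a minimum of 14 completers, 16 planned and a ceiling of 20. It gives two levels, "Significance (p<0.01 or p<0.05, corrected", so both are used below, two-sided. It does not say whether the SD is per visit or of the paired difference. I take the SD of the difference as 10, or as 10 × √2 = 14.14 (SD 10 per visit, zero correlation). Period effects of 2.5, 5 and 10 points and all sequence splits are assumptions.

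**1. The plan's own figure.** The minimum of 14 reproduces in two ways; the document does not say which was used.
- Two-group normal formula at 0.05: 2 × (1.960 + 0.842)² × (10/15)² = 6.98, so 7 per group and 14 in total.
- Paired t-test at 0.01 with SD of the difference 14.14: 14 subjects, power 0.81.

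**2. What the paired difference contains.** With drug reading D, placebo reading P and the single baseline B, (D − B) − (P − B) = D − P. Expressed as a percent of baseline it is (D − P)/B. Either way the comparison is Visit 4 against Visit 8, 71 − 22 = 49 days apart, and the baseline removes no period effect. Let π be the mean shift from period 1 to period 2. The expected difference is effect + π if drug comes second and effect − π if drug comes first.

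**3. Precision, 8:8.** The variance of the paired differences is inflated by 1 + (16/15)(π/SD)². For example, 1 + (16/15)(5/10)² = 1.27. Mean 95% interval widths are from simulation at the 5% level.

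| π | Width, SD 10: without / with term | Width, SD 14.14: without / with term | Variance inflation, SD 10 / 14.14 |
|---|---|---|---|
| 2.5 | 10.8 / 10.5 | 15.1 / 14.9 | 7% / 3% |
| 5 | 11.8 / 10.5 | 15.8 / 14.9 | 27% / 13% |
| 10 | 15.1 / 10.5 | 18.4 / 14.9 | 107% / 53% |

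**4. Power at 15 points, 8:8, SD 14.14, without vs with the term.**
- π = 10: 0.93 vs 0.98 at level 0.05, and 0.71 vs 0.87 at 0.01.
- π = 5: 0.968 vs 0.976 at 0.05, and 0.84 vs 0.87 at 0.01.

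With SD 10, π = 10 and level 0.05, power is 0.996 vs 1.000.

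**5. Unequal completers.** The bias is π × (n1 − n2)/(n1 + n2). At 10:6 the factor is 4/16 = 0.25, giving 0.6, 1.25 and 2.5 points for π = 2.5, 5 and 10. At 9:7 it is 2/16, giving 0.6 and 1.25 points for π = 5 and 10.

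**6. Type I error of the plain test.** At 8:8 it is conservative: 1.7% at a nominal 5% (SD 14.14, π = 10). At 9:7, 10:6 and 9:5 the two-sided error is at most about 5.2%. At 11:5, with π of 5 to 10, the tail favoured by the bias alone reaches 5.9% to 10.1%. These rates are conditional on the split.

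**7. How likely are unequal splits?** If 20 subjects start at 10:10 and four drop out at random, the chances are 42% for 8:8, 50% for 9:7 and 9% for 10:6; 11:5 cannot occur. Under simple randomisation with 16 completers, 10:6 has a 24% chance and 11:5 or worse 21%.

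**The case against.** The strongest reply is that a paired t-test is a recognised cross-over analysis and no section points to a period effect. Tremor medication must be stable for six weeks before screening and is checked at follow-up, and a taper and washout separate the periods. A 10-point period effect would be two-thirds of the planned treatment effect. All of this stands, and it is why the point is an improvement and not an error. These safeguards limit carry-over and some drift, but they do not remove practice or time effects.

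Adjustment is also not always the gain. With π = 2.5 at 10:6 it widens the interval slightly: 10.8 to 10.9 (SD 10) and 15.1 to 15.4 (SD 14.14). At 11:5, SD 14.14 and π = 5, it goes from 15.7 to 16.1. In those cases the benefit is an estimate free of the period bias, not a narrower interval.

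The inflated SD matters only if a later cross-over is sized on the unadjusted value. Sequence is known from the randomisation, so an adjusted SD could be computed afterwards. Section 9.8 also leaves the analysis to a consulting statistician, who could add the term. Neither possibility amounts to specifying it in advance.

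A reader might infer from the 9.8 wording that each condition will be tested separately against baseline, so that the 9.6 comparison is never made. The documents do not support that as a finding. The phrase can be read as drug change against placebo change, which matches 9.6 and Hypothesis 1, and no decision rule based on separate tests is stated. It is loose wording worth tightening, not a contradiction.

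**Conclusion.** The point holds as a low-priority improvement. Section 9.8 omits a period term, and the single screening baseline cannot stand in for one. The consequences are a wider interval, an inflated SD and, only with unequal completers, a biased estimate. At the planned 15-point effect and the 5% level the power loss with balanced sequences is small. It becomes material at the 1% level with a large period effect (0.71 vs 0.87).

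A reader might infer that the planned test is invalid or produces too many false positives. That does not follow. It is unbiased with balanced sequences, holds its level averaged over random splits, and its two-sided error is not materially inflated except at splits as extreme as 11:5. Nor do the figures show that the sample size is wrong.

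Every size given depends on assumed period effects and splits and on the two readings of the 9.7 SD. If there is no period effect, nothing is lost by the plan as written.

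**What to change.** Replace the test sentence in 9.8 with: 'The primary test is the within-subject drug-minus-placebo difference in change from baseline in spirography tremor power (Visits 4 and 8), adjusted for period by a two-sequence period-adjusted paired analysis or an equivalent mixed model, reported with a 95% confidence interval. Comparisons of each condition with screening are descriptive.'

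This needs no new visits or data. If there is no period effect, the cost is one degree of freedom and some power when sequences are unequal. For an 8-point effect, SD of the difference 10, n = 16 and level 0.05, power goes from 0.848 to 0.845 at 8:8, 0.821 at 10:6 and 0.788 at 11:5. With a small period effect and unequal sequences the interval can be slightly wider. At level 0.01 with SD 14.14 the minimum rises from 14 to 15 (power at 14 is 0.798 instead of 0.81). The planned 16 completers cover that.

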10. HUMAN SUBJECTS

10.1 Subjects

Description of Study Population

16 patients with Clinically Definite or Clinically Probable ET will complete the study. We will have an accrual ceiling of 20 to allow for dropouts. This will be a single site investigator-initiated trial with all aspects of the study taking place at UCSD. Subject selection will be equitable among adult men and women. We plan to enroll a wide selection of ages (\geq 21) and ethnicities to enhance our sample diversity and generalizability. Pregnant or lactating females will be excluded due to the unknown teratogenicity of THC/CBD. Any women of childbearing potential will undergo a urine pregnancy test prior to receiving study medication and will be required to use some form of contraception during the course of the trial.

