9.3 Description of Screening and Study Design

SCREENING VISIT

After being screened for inclusion/exclusion criteria and providing informed consent, subjects will undergo a complete neurological examination to confirm their diagnosis of ET and exclude other neurological disorders. Additional measures collected during this visit are listed in Appendix 1. Note that subjects will need to have been on a stable dose of their medications for a minimum of 6 weeks prior to the screening visit and will be

encouraged to remain on these doses for the remainder of the study period. Subjects will be asked about their other tremor medication doses at each follow-up visit to confirm stable doses.

VIDEOTAPED TETRAS

As part of each study visit (1-3), subjects will complete a TETRAS rating scale while being videotaped. This is intended for rating purposes by two blinded raters at the completion of the study.

RANDOMIZATION

After completion of the screening visit, subjects will be assigned to one of two possible treatment arms based on a pre-set randomization matrix. Only the research pharmacy who will be responsible for dispensing the doses will be aware of which of two treatment options will be provided, but not the identity of the particular agent. The equivalence of the THC/CBD and Placebo will be equally matched by the manufacturer, making it difficult for the subject to discriminate which arm they are on. Subjects will be asked which arm they are receiving at each assessment visit and on telephone follow up to assess for potential unblinding.

DOSE TITRATION AND TREATMENT

On visit 1 and 5, subjects will receive 1 capsule of IMP every morning. On visit 2 and/or 6, if the subject tolerated 1 capsule then they would receive 2 capsules every morning. Alternatively, if 1 capsule was not tolerated, the timing of the administration would be changed to 1 capsule in the evening. At visit 3 and/or 7, if the single nightly capsule was not tolerated, the subject would be dropped at this visit. If the 2 capsules every morning were tolerated, the subject would then receive 2 capsules in the morning and 1 capsule in the evening. If 2 capsules in the morning were not tolerated, the subject dosing would be changed to 1 capsule in the morning and 1 capsule in the morning and 1 capsule nightly. Subjects will remain on the highest tolerable dose for the duration of the period until visit 4 or 8 (See Appendix 2).

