15. RISK MANAGEMENT PROCEDURES AND ADEQUACY OF RESOURCES

Subject safety and tolerability will be monitored in this study across multiple dimensions by tracking clinical adverse events; vital signs (including orthostatic pulse and blood pressure); general and neurological physical examinations; standard clinical laboratory safety panels for complete blood counts, chemistry, coagulation, and urinalysis; standard 12-lead electrocardiograms; the Patient Reported Outcomes of the Common Terminology Criteria for Adverse Events (PRO-CTCAE), and Columbia Suicide Severity Rating Scale (C-SSRS). Subjects answering "yes" to Suicidal Ideation item 4 or 5 on the C-SSRS during the study must be withdrawn from the study treatment. The PI will also withdraw subjects from treatment if, in the judgment of the Investigator, the subject develops other indicators of significant risk of suicide. In the event that suicidal ideation is observed in any study subject, the PI will manage the situation as he/she deems medically and psychiatrically appropriate. Further, In the event that a subject reports suicidal ideation, the subject will be withdrawn from the study and personally escorted by a study team member to the UCSD Emergency department for urgent psychiatric evaluation and management. In the event that we are made aware of such suicidal ideation by telephone outside of routine study visits, subjects will be referred to a local ED for evaluation and we will conduct a telephone follow up to ensure the subject followed through with these recommendations.

The specified inclusion/exclusion criteria have been carefully considered to avoid enrollment of subjects for whom exposure to the study drug might pose a hazard, particularly as it relates to individuals with a history of substance abuse.

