APPENDIX 1: STUDY OVERVIEW

EVENT	VISIT 0: SCREENING	VISIT 1: DOSE TITRATION	VISIT 2: PK	VISIT 3: PK	TREATMENT PHASE	VISIT 4: ASSESSMENT	TAPER	WASHOUT	VISIT 5: DOSE TITRATION	VISIT 6: PK	VISIT 7: PK	TREATMENT PHASE	VISIT 8: ASSESSMENT	TAPER	TELEPHONE FOLLOW-UP	TOTAL DAYS
TOTAL DAYS	0	ų	5	1	16	1	5	22	ų	5	1	16	1	5	1	77
DAY NUMBER (±3)	0	1	3	6		22	23	28	50	52	55		71	72	77	
Consent	х															
Neurological Exam	х					x							х			
Vital Signs	х	х	Х	x		х			х	х	x		х			
TETRAS (video)	х					х							х			
Spirography	Х					X							Х			
Accelerometry	Х					Х							Х			
CGI/PGI						Х							Х			
PRO-CTCAE	х	x	х	x		х			x	х	x		х		х	
C-SSRS	Х					Х							Х		Х	
Lab Testing - pregnancy, CBC, CMP, Drug screen	x					x							x			
EKG*	x	x	x	x		x			x	x	x		x			
PK Sample(s)			Х	x		X				x	х		х			

* EKG at screening, then post-dose at each subsequent visit.

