9.16.3 APPENDIX 3: PHARMACOKINETIC SAMPLING TIMES**

DAY #	TIME
3	Trough
6	Trough
22	Trough + Pseudorandom (1,2,3,
	or 4 hrs/post-dose) sample

**NOTE: Samples will be collected for drug and placebo to maintain blinding, but PK lab will be unblinded in order to process only drug samples. If subject receive placebo first, PK days will be: #52, 55, and 71.

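### Minor, low-cost safety improvement: add a urine pregnancy test at Visit 5 (day 50), where dosing restarts and the last scheduled test is 28 days old

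*Combined protocol and SAP*

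**What the plan says.** Section 10.1 states: "Any women of childbearing potential will undergo a urine pregnancy test prior to receiving study medication". It also requires contraception throughout and gives unknown teratogenicity as the reason for excluding pregnant women. Section 14 adds that a negative test is needed before participation and that the investigators want no fetus exposed unnecessarily, although it also says that THC and CBD are not known to cause birth defects.

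Section 9.3 starts dosing twice: "On visit 1 and 5, subjects will receive 1 capsule of IMP every morning". Between the two starts there is a one-week taper, and then: "Subjects will then complete a 3-week washout period prior to being crossed-over to the alternate arm". Appendix 3 confirms that placebo-first subjects have their active period second: "If subject receive placebo first, PK days will be: #52, 55, and 71".

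In Appendix 1 the row "Lab Testing - pregnancy, CBC, CMP, Drug screen" is marked at Visits 0, 4 and 8 only. The C-SSRS is marked at those three visits and at the day-77 telephone call. At Visit 5 the marked items are vital signs, PRO-CTCAE and EKG, and the EKG is post-dose by the footnote ("EKG at screening, then post-dose at each subsequent visit").

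Section 15 requires withdrawal of a subject who answers yes to suicidal ideation "item 4 or 5 on the C-SSRS during the study must be withdrawn from the study treatment".

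**The concern.** In a cross-over trial, each period's first dose is a new exposure decision. For placebo-first women, the screening test made just before Visit 1 precedes placebo. The test that precedes their first THC/CBD is the Visit 4 test, taken before about four weeks of taper and washout. A pregnancy conceived in that interval would not be looked for before Period 2 dosing, and the next scheduled test is at Visit 8. What is at stake is avoidable fetal exposure in a very small number of women, which the protocol says it wants to prevent. The primary endpoint, sample size and efficacy analysis are not affected.

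**Working it through.** **Inputs from the documents**
- Visit days (Appendix 1, ±3 days): Visit 0 = 0, Visit 1 = 1, Visit 4 = 22, Visit 5 = 50, Visit 8 = 71.
- Taper of 1 week and washout of 3 weeks (section 9.3).
- 16 completers, ceiling of 20 (section 9.7). Section 9.2 places an emphasis on equal numbers by sex and equal numbers above and below age 50.

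**Reading of the table.** The day row, the lab row and the C-SSRS row each split into 17 cells, matching the 17 column headings, so the marks can be assigned to visits. The Visit 5 cell is empty in both the lab row and the C-SSRS row. It is also empty in both rows at Visit 1.

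**Reproducing the interval.** Visit 4 to Visit 5 is 50 − 22 = 28 days. Section 9.3 gives the same total: 7 + 21 = 28.

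**Age of the last pregnancy test at first dose**
- Period 1: 1 − 0 = 1 day nominal. If both windows apply in full, the most is 4 − (−3) = 7 days.
- Period 2: 28 days nominal, from 47 − 25 = 22 to 53 − 19 = 34 days.

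**First dose to next test**
- Period 1: 22 − 1 = 21 days.
- Period 2: 71 − 50 = 21 days (68 − 53 = 15 to 74 − 47 = 27).

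Follow-up after dosing begins is therefore the same in both periods. Only the age of the pre-dose test differs.

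**How many women.** The documents do not give the number of childbearing potential. As a rough proxy, take women under 50 and assume the sex and age splits are independent: 16 × 0.5 × 0.5 = 4, or 20 × 0.5 × 0.5 = 5. This is not a bound. The equal splits alone allow 0 to 8 of 16, or 0 to 10 of 20.

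**Expected conceptions in 28 days.** With *n* women and assumed annual contraceptive failure *f*: n × [1 − (1 − f)^(28/365)].

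| n | f = 1% | f = 10% |
|---|---|---|
| 4 | 0.0031 | 0.032 |
| 5 | 0.0039 | 0.040 |
| 10 | 0.0077 | 0.080 |

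Assuming 1:1 allocation, half fall in placebo-first women: 0.0031 / 2 ≈ 0.0015 to 0.040 / 2 = 0.020 for 4 to 5 women, and 0.080 / 2 = 0.040 at the extreme of 10.

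**After the change.** A test at Visit 5 before the capsule brings the age of the last test at Period 2 dosing from 28 days to 0.

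**The case against.** The strongest reply is that nothing in the plan is wrong. The day-0 and day-22 tests both come before Period 2, the entry condition in section 14 is met, and no maximum age is set for a test. That stands. A reader might infer that section 10.1 is breached at Visit 5; its wording does not support that.

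A reader might also infer that Period 1 has a pre-dose check which Period 2 drops. It does not: Visit 1 has no test of its own and relies on eligibility screening one nominal day before. The difference lies in how old the last test is.

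The risk figures are tiny and rest on stacked assumptions. Women under 50 overstates the number of childbearing potential, and a disorder that section 7.1 shows to be more common at 65 and over may recruit older. Active-first women receive placebo in Period 2, so the exposure argument does not apply to them. All of this stands and keeps the point minor. Contraception lowers the risk but does not detect a pregnancy.

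The tempting stronger reading is that the missing C-SSRS at Visit 5 is an equal gap that leaves the withdrawal rule without effect from day 22 to day 71. The documents do not support that. No C-SSRS is scheduled in those 49 days, and the Period 1 taper has no counterpart to the day-77 C-SSRS that follows the Period 2 taper. But section 15 also requires withdrawal on any reported ideation, covers ideation learned of by telephone outside visits, and allows withdrawal if "in the judgment of the Investigator, the subject develops other indicators of significant risk of suicide". Section 10.2 excludes anyone with active or prior ideation, and PRO-CTCAE is collected at Visit 5. The benefit of an extra C-SSRS has not been quantified.

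Finally, the documents give no costs, so calling the change cheap is a judgement. For the urine test it is a safe one, because Visit 5 is already an on-site visit.

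**Conclusion.** The point holds as a minor participant-safety improvement. At the restart of dosing the last pregnancy test is nominally 28 days old (22 to 34 with windows), and for placebo-first women this is the last test before their first THC/CBD. Expected conceptions in those women over the interval are about 0.0015 to 0.02, assuming 1:1 allocation, 4 to 5 women under 50 and 1% to 10% annual contraceptive failure. The figure reaches about 0.04 if 10 of 20 subjects are such women and failure is 10%. The argument is that the check is nearly free and serves an aim the protocol already states; it does not depend on the harm being likely. The table reading and day arithmetic are firm. The case counts are illustrative. The C-SSRS is secondary and optional.

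**What to change.** - In Appendix 1, mark a urine pregnancy test at Visit 5 for women of childbearing potential, to be done before the first Period 2 capsule. Keep the Visit 4 test.
- In section 10.1, state that a negative test precedes the first dose of each period and that Period 2 dosing is withheld if the test is positive.
- Optional: add a C-SSRS at Visit 5 before dosing, with the existing section 15 rules applied to the result.

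The pregnancy test costs one extra urine test for a few women (roughly 4 to 5 on the assumptions above) at a visit that already takes place. A very recent conception can still be missed, so the gap is narrowed and not closed. The optional C-SSRS would add 16 to 20 interviews by a certified rater. Endpoints, sample size and number of visits stay the same.
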